# **5.4.4** Cycle 1, Day 16 | Phase Ib Arm 2 Only

- Phase Ib Arm 2 Only: Blood samples for pharmacokinetics (see Section 6.4).
- Assess adverse events

# **5.4.5** Cycle 1, Day 22

- Vital signs, Weight
- Assess adverse events
- Record concomitant medication

# 5.5 On-Study Evaluation & Assessment Schedule | Cycle 2

## **5.5.1** Cycle 2, Day 1

For both Phase Ib and Phase II, patients will have the following assessments:

- Vital signs (weight, temperature, blood pressure, respiration and pulse)
- ECOG performance status
- Physical examination
- Hematology (see Section 6.3)
- Blood chemistry (see Section 6.3)
- Urinalysis (see Section 6.3)
- Serum AFP (see Section 6.3)
- Assess adverse events
- Record concomitant medication
- Dispense 28 day supply study drug (either BBI608 or BBI503)\*

\*2 days of "extra doses" may be re-dispensed at a monthly visit if it was needed during the preceding cycle

#### **5.5.2** Cycle 2, Day 15

Patients receiving BBI608 should take their dose of protocol therapy in clinic on this day.

- Vital signs, Weight
- Assess adverse events
- Record concomitant medication

- Blood samples for pharmacokinetics (Section 6.4)
- Phase Ib Only: Electrocardiogram approximately 3.5 hours after morning dose of BBI608 or approximately 13 hours after previous night dosing of BBI503
- *Phase II:* Electrocardiogram at least 3.5 hours after morning dose of BBI608 if patient has been taking the doses regularly, otherwise this assessment would be moved to C3D1 or subsequent visit. The electrocardiogram is required for patients on all arms. Optional on-treatment tumor biopsy\*

\*If the optional on-treatment tumor biopsy is scheduled on a day other than when pharmacokinetic blood drawn are obtained, then a single blood draw for determination of plasma study drug levels is required at the time of the biopsy. The on-treatment biopsy can be performed beyond the window for the visit due the complexity of the procedure.

# 5.6 On-Study Evaluation & Assessment Schedule | Cycle 3 and Subsequent Cycles

# **5.6.1** Cycle 3, Day 1 (and Day 1 of all subsequent study cycles)

The following assessments will also be performed:

- Vital signs (weight, temperature, blood pressure, respiration and pulse)
- Physical examination
- ECOG performance status
- Hematology (see Section 6.3)
- Blood chemistry (see Section 6.3)
- Urinalysis (see Section 6.3)
- Serum AFP (see Section 6.3)
- Assess adverse events
- Record concomitant medication
- Dispense study drug (either BBI608 or BBI503) (28 day supply) \*

## **5.6.2** Cycle 3, Day 15 (and Day 15 of all subsequent cycles) \*

- Vital signs, Weight
- Assess adverse events
- Record concomitant medication

#### **5.7** Tumor Evaluation Visits

#### **5.7.1** Baseline

Baseline radiologic evaluation of chest, abdomen, and pelvis of sufficient quality to determine presence of disease according to RECIST and mRECIST for HCC is required prior to starting protocol therapy. This is defined as computed tomography (CT) with intravenous contrast of the chest, abdomen, and pelvis with tri-phasic liver scan. For those with an allergic reaction to intravenous CT contrast despite appropriate pre-treatment measures, magnetic resonance imaging (MRI) of the abdomen and pelvis with gadolinium plus a non-contrast CT scan of the chest is required.

\*2 days of "extra doses" may be re-dispensed at a monthly visit if it was needed during the preceding cycle

\*These study visits do not need to be in-person. If a patient is not seen in-person, he or she should be contacted by phone in order to assess adverse events and record concomitant medication. Vital signs and weight need only be obtained if there is an in-person visit.

Radiologic assessments satisfying the above requirements that are obtained within 14 days of the first dose of sorafenib (Cycle 1, Day 1) may be used as baseline imaging.

#### **5.7.2** Per-Protocol

Per-protocol radiologic assessments will be performed every eight weeks (56 days), as calculated according to the date of the first dose of the sorafenib run-in period. A window of ±7 days is allowed when scheduling radiologic disease assessments (applies to each scan individually). Per-protocol radiologic assessments are defined as a computed tomography (CT) with intravenous contrast of the chest, abdomen, and pelvis with tri-phasic liver scan. For those with an allergic reaction to intravenous CT contrast despite appropriate pre-treatment measures, per-protocol evaluation with magnetic resonance imaging (MRI) of the abdomen and pelvis with gadolinium plus a non-contrast CT scan of the chest is required.

Additional radiologic evaluations when clinically indicated are allowed. However, evaluations obtained for clinical indications cannot be substituted for per-protocol radiologic assessments unless they also satisfy the above per-protocol definition of radiologic assessment.

Per-Protocol radiologic evaluations should be performed every 8 weeks (56 days) until radiologic disease progression is observed according to *both* RECIST 1.1 and modified RECIST for patients with HCC. If protocol therapy is permanently discontinued for any reason without documentation of PD per RECIST 1.1 and mRECIST for HCC, per-protocol imaging evaluations should continue every 8-weeks until criteria for disease progression are satisfied according to both RECIST 1.1 and mRECIST for HCC.

Patients with an imaging assessment which meets criteria for either complete response (CR) or partial response (PR) according to RECIST 1.1 or mRECIST should have a repeat, confirmatory, radiologic assessment approximately 4 weeks after the assessment in which CR or PR criteria were met. After the confirmatory image, radiologic assessments return to the every 8 week schedule.

If, at any time, a determination is made for a study subject to discontinue protocol therapy, the treating investigator should determine the likelihood that the patient will be able to attend the next scheduled radiologic assessment. If the treating investigator feels it is unlikely that a patient will be able to obtain the next scheduled per-protocol radiologic assessment, a per-protocol radiologic assessment should be obtained as soon as possible (a minimum of 4 weeks, however, should elapse between per-protocol assessments).

Tumor response will be evaluated using the guidelines for Response Evaluation Criteria in Solid Tumors (RECIST 1.1) and modified RECIST for patients with HCC. Highlights of these guidelines are contained in Section 9.

In general, for each radiologic imaging assessment obtained during the study, the following information and documentation is required:

- Completed RECIST 1.1 and mRECIST for HCC worksheets (provided by Sponsor) that document lesion measurements and descriptions
- De-identified, dictated, radiology report of the image (see Section 5.7.4)

De-identified digital images and/or complete copies of the digital imaging study may be requested from study sites (see Section 5.7.4).

### **5.7.3** Patient Disposition & RECIST Criteria

RECIST criteria serve to categorize clinical radiologic images. RECIST categorization alone should not determine continuation or discontinuation of protocol therapy in a patient. Given that both study drugs (BBI608 and BBI503) have a unique mechanism of action that targets cancer stem cells, study drug therapy may be continued in a patient who is clinically well but who meets criteria for "Progressed Disease" per RECIST (either RECIST 1.1 or modified RECIST for patients with HCC). Continuation of study drug (either BBI608 or BBI503) therapy in this context is allowed provided that no further standard, approved

treatment options exist, and provided that the investigator concludes that the potential benefit to the patient outweighs the potential risk.

# **5.7.4** Documentation and Digital Files

Clinical site staff will be responsible for collection and documentation of those lesion measurements required to complete response assessments according to RECIST 1.1 guidelines and modified RECIST guidelines for patients with HCC. Worksheets will be provided on which measurements for target and non-target lesions using both RECIST 1.1 and mRECIST for HCC can be documented. Please refer to Section 9 for further information on definitions and RECIST guidelines.

Quantitative image measurements and qualitative image characteristics according to RECIST guidelines will be documented in study Case Report Forms (CRFs). For exploratory purposes, the Sponsor may collect additional information from patient radiologic images. Examples of additional information include but are not limited to: de-identified radiology reports or dictations, digital copies of de-identified radiologic images, and/or complete de-identified image files.

### 5.8 End of Study Evaluation

For both phase Ib and phase II, all patients should be seen 14 to 30 days after discontinuation of protocol therapy. This is the End of Study (EOS) visit. The following assessments will be made during the end of study visit:

- Physical examination
- ECOG performance status
- Vital signs (weight, temperature, blood pressure, respiration and pulse)
- Hematology (see Section 6.3)
- Blood chemistry (see Section 6.3)
- Urinalysis (see Section 6.3)
- Serum AFP (see Section 6.3)
- Assess Child Pugh Class
- Tumor measurements and staging if radiologic progression has not yet been documented on study. That is, if a patient discontinues protocol therapy due to radiologic progression of disease, an End of Study *imaging* assessment is not required.
- Assess adverse events
- Record concomitant medications

Patients who are identified at the EOS visit as having persistent adverse events related to study drug (either BBI608 or BBI503) should continue to be followed on a monthly basis (or more frequently if clinically indicated) until resolution of study drug - related adverse events or until the AEs are deemed irreversible.

Any Serious Adverse Events (SAEs) that occur up to 30 days after the last dose of study drug (either BBI608 or BBI503) will be reported to the Sponsor regardless of assessed causality (also see Section 8.2).

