#### Note:

Once the amendment 3 is in effect, Arm 2 in the Phase II portion will be closed for enrollment due to BBI503 portfolio priorities and to increase efforts in enrolling patients on to Arms 1 and 3.

At the time of the amendment 3 being in effect, there were approximately 10 subjects already enrolled in Arm 2. Therefore, the actual sample size in Phase II in the end is projected to be approximately 70 patients after the amendment 3

Pharmacodynamic assessments will be performed in patients with readily accessible tumors through an optional on-study tumor biopsy. Archival tissue, if available, will be collected from all patients.

Throughout the study, safety and tolerability of BBI608 in combination with sorafenib and of BBI503 in combination with sorafenib will be assessed for the duration of study treatment and up to 30 days after discontinuation of study drug (either BBI608 or BBI503).

Evaluation of anti-tumor activity will be performed at regular 8—week intervals, with the first assessment 8 weeks (56-days) after Cycle 1, Day 1. The radiologic assessments will be evaluated according to RECIST 1.1 and modified RECIST (mRECIST) for patients with HCC. Alpha-feto protein (AFP) measurement will be performed at baseline, at the end of the 2-week sorafenib monotherapy Run-In, and at the start of each subsequent study cycle.

A patient may continue protocol therapy beyond progression that is determined by RECIST criteria (either RECIST 1.1 or mRECIST for patients with HCC), provided that the patient is obtaining potential clinical benefit in the opinion of the investigator. If sorafenib is discontinued due to sorafenib-related toxicities, study drug (either BBI608 or BBI503) may be continued.

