# **5.9.1** Dates Associated with Discontinuation from Study

The following clarifies important dates at the end of study treatment:

Date of Last Dose: The date that the last dose of study medication is taken (either BBI608 or

BBI503). The Date of Last Dose does not necessarily need to be the Date

Off Active Study.

Date Off Active Study: The date when both the patient and the investigator/study team understand

the patient to be off of active protocol treatment. In most cases, this will be the same as the *Date of Last Dose*; however, it does not need to be the case. In addition, the *Date Off Active Study* may not coincide with a formal study

visit.

End of Study Visit: A formal study visit held 14 to 30 days after the *Date of Last Dose*.

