### 5.10 Follow Up After Treatment Discontinuation

For both the phase Ib and phase II portions of the study, the follow-up phase of the study will begin after the EOS study visit has been completed. Patients will be followed for specified clinical endpoints (both primary safety and secondary exploratory efficacy endpoint), and other important information such as post-protocol therapy.

As specified in Section 5.7.2, per-protocol imaging (every 8 weeks/56 days) should continue until criteria for disease progression according to both RECIST 1.1 and mRECIST for HCC are met.

There are no further visits required specifically for the study after the EOS visit, with the exception of radiologic assessments every 8 weeks until progression of disease is documented according to both RECIST 1.1 criteria and mRECIST for patients with HCC criteria.

The clinical parameters and endpoints for follow-up after a patient permanently discontinues study drug (either BBI608 or BBI503) administration are specified in table below, as is the recommended follow up frequency. Follow-up and information collection is intended to be accomplished through review of the local medical record system by site study staff and/or study CRAs-Monitors. Contact with the primary oncologist and/or primary care physician for a given patient may also be required.

Table 3: Clinical Parameters for Post-Protocol Therapy Follow-Up

Endpoint	Description	Follow-Up Frequency
Performance Status Decline	First date when ECOG performance status of $\geq 3$ is documented, if possible	Evidence for clinical endpoints
Subsequent Therapy	Names and dates of anti-cancer treatment administered after permanent study drug (either BBI608 or BBI503) discontinuation. "Clinical Trial" can also be used if agent name is not publically available	will be assessed monthly for the first 6 months after discontinuing study drug (either BBI608 or BBI503)  Then,  Quarterly from 6 months to 18
Objective Disease Progression following subsequent therapy	Date criteria for RECIST 1.1 and/or mRECIST for HCC categorization of "PD" are met after starting any post-protocol therapy, if possible*	months after discontinuing study drug (either BBI608 or BBI503)  Then,  Semi-annually thereafter
Survival	Date of death due to any cause	Semi-aminary mereaner

\*Passive follow-up only of radiologic imaging obtained following initiation of any post-protocol therapy

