### 10.6 Safety Analysis

Safety and adverse events will be summarized for all enrolled patients in the phase Ib portion, phase II portion, and for the study overall. In addition, all patients receiving at least one dose of study drug (either BBI608 or BBI503) will be considered in the study drug safety population. Safety and adverse events will be summarized for the study drug safety population of phase Ib, phase II, and overall.

During the phase Ib portion of the study, adverse events will be summarized by dose-level and overall by arm. The numbers of patients enrolled, number with DLT, and number evaluable for determination of dose-escalation at each dose-level by arm will be reported. In addition to the evaluation and categorization of adverse events, listings of laboratory test results collected at baseline and during the study will be generated. Descriptive statistics summarizing the changes in those laboratory tests over time will be presented.

Adverse events will be graded according to the NCI CTCAE, version 4.0. The incidence of adverse events will be evaluated for each cohort. Patients will be followed for adverse events for at least 30 days after the last dose of study drug (either BBI608 or BBI503), or until they have recovered from all related study drug (either BBI608 or BBI503) adverse events.

Safety and adverse events will be reported by study arm for the intent to treat population and for all enrolled patients during the phase II portion of the study.

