7.2.4.1. Adverse Events

Overall Summary of AEs

An AE will be regarded as **treatment-emergent**, if:

- it occurs on the day of or after the first dose of napabucasin or amcasertib or a combination drug and up to 30 days after the last dose of any study drug; or
- it occurs prior to first dose date of napabucasin or amcasertib or a combination drug and worsens in severity on therapy and up to 30 days after the last dose of study drug.

Adverse events will be coded by SOC and PT using the MedDRA v19.0. The severity of AEs will be graded by the investigator using (NIH NCI CTCAE Version 4.0). The verbatim term will be included in the AE listings.

An overview of treatment-emergent adverse events (TEAEs) will be provided. The number and percentage of patients will be summarized for:

- Patients with at least one TEAE
- Patients with TEAEs of CTCAE Grade 3 or higher
- Patients with serious TEAEs
- Patients with napabucasin-related TEAEs

- Patients with napabucasin-related TEAEs of CTCAE Grade 3 or higher
- Patients with amcasertib-related TEAEs
- Patients with amcasertib-related TEAEs of CTCAE Grade 3 or higher
- Patients with sorafenib-related TEAEs
- Patients with sorafenib-related TEAEs of CTCAE Grade 3 or higher
- Patients with napabucasin-related serious TEAEs
- Patients with napabucasin-related serious TEAEs of CTCAE Grade 3 or higher
- Patients with amcasertib-related serious TEAEs
- Patients with amcasertib-related serious TEAEs of CTCAE Grade 3 or higher
- Patients with sorafenib-related serious TEAEs
- Patients with sorafenib-related serious TEAEs of CTCAE Grade 3 or higher
- Patients with TEAEs leading to napabucasin dose hold
- Patients with TEAEs leading to dose reduction of napabucasin
- Patients with TEAEs leading to amcasertib dose hold
- Patients with TEAEs leading to dose reduction of amcasertib
- Patients with TEAEs leading to sorafenib dose hold
- Patients with TEAEs leading to dose reduction of sorafenib

Summary of AEs during Run-in Period

Besides overall summary of AEs as described above, the analysis of AEs during Run-in period will be summarized separately. Run-in Period is defined from the first sorafenib dose date to one day prior to patient administrated the napabucasin/amcasertib, or to the end of treatment if patient discontinued the study treatment before the napabucasin/amcasertib administration. For Phase II sorafenib monotherapy arm patients, run-in period is defined as the first 14 days of sorafenib administration.

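### An End of Study visit held before day 30 leaves up to 16 of the 30 post-treatment days with no scheduled contact asking about new non-serious adverse events

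*Protocol*

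**What the plan says.** **Visit.** Protocol 5.8 sets the EOS visit so that "all patients should be seen 14 to 30 days after discontinuation of protocol therapy", and AE assessment is one of its items. Section 5.9.1 describes it as "A formal study visit held 14 to 30 days after the" date of last dose, and defines that date by BBI608 or BBI503. Appendices A and B show the same 14 to 30 days and no later AE assessment column.

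**After the visit.** Section 5.10 states: "There are no further visits required specifically for the study after the EOS visit, with the exception of radiologic assessments every 8 weeks", continuing until progression. Table 3 lists four follow-up items: performance status decline, subsequent therapy, progression after subsequent therapy, and survival. They are to be gathered mainly from the medical record, monthly for the first six months. AEs are not among them.

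**Counting window.** Protocol 10.6 says: "Patients will be followed for adverse events for at least 30 days after the last dose of study drug". SAP 7.2.4.1 treats an AE as treatment-emergent "up to 30 days after the last dose of any study drug".

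**Provisions that continue past EOS.** Section 5.8 requires monthly follow-up of persistent AEs related to BBI608 or BBI503. Sections 5.8 and 8.2.2 require serious AEs to be reported to 30 days whatever their cause. Section 8.1.1 extends AE documentation into the post-treatment follow-up period. Section 8.1.2 says patients should be told to report AEs and that follow-up AEs go on the case report form.

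**The concern.** The schedule and the counting rule do not match. A site may hold EOS on day 14 and still be within the visit window, while the analysis takes AEs up to day 30. A patient with no persistent related AE at that visit then has no scheduled visit, call or Table 3 item that asks whether anything new has happened.

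The events exposed are new non-serious AEs. Serious ones have their own reporting rule, but a Grade 3 event need not be serious. This matters because tolerability and safety are in the Phase II primary objective. The proportion of patients with Grade 3 AEs, with a 95% confidence interval, is one of the two quantities that Protocol 10.5 and SAP 3.2.3 name for Phase II estimation. A patient last asked on day 14 enters that proportion on the same footing as one last asked on day 30.

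**Working it through.** The plan states no figure for this point, so there is none to reproduce. The check is date arithmetic on the documents' own windows.

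**Inputs**
- EOS visit: day 14 to day 30 (Protocol 5.8, 5.9.1, Appendices A and B).
- AE window: day 30 (Protocol 10.6; SAP 7.2.4.1).
- Target of about 30 patients in each of Arms 1 and 3 (Protocol 10.3).
- Expected treatment of 4 to 24 weeks (Protocol Synopsis, Duration of Treatment).

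**Step 1: days without scheduled solicitation.** Gap = 30 − EOS day, with both windows counted from the same last dose.

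| EOS day | Gap (days) | Share of the 30 days |
|---|---|---|
| 14 | 30 − 14 = 16 | 16/30 = 53% |
| 21 | 30 − 21 = 9 | 9/30 = 30% |
| 30 | 30 − 30 = 0 | 0% |

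**Step 2: share of the whole treatment-emergent window.** The SAP window opens at first dose. Taking 4 to 24 weeks as the time on treatment, it lasts 28 + 30 = 58 days to 168 + 30 = 198 days. The worst-case gap is then 16/58 = 28% down to 16/198 = 8%, all of it after the last dose.

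**Step 3: weight of one event.** With 30 patients in an arm, one missed event in a patient with no earlier Grade 3 event moves the Grade 3 proportion by 1/30 = 3.3 percentage points. A second Grade 3 event in the same patient moves it by nothing. The documents give no AE rate for days 15 to 30, so the expected number missed cannot be calculated.

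**Step 4: the anchor.** Step 1 assumes a single last-dose date, but the texts differ:
- Section 5.8 counts the visit from stopping protocol therapy.
- Sections 5.9.1 and 10.6 count from BBI608 or BBI503, which Arm 3 never receives.
- The SAP counts from any study drug.

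Section 4.3 lets Arm 1 and Arm 2 patients receive sorafenib after study drug stops. Suppose that sorafenib counts as study drug in the SAP rule. This is an assumption, though SAP 5.2 does count sorafenib dosing for the safety set. If it is taken for x days beyond the last BBI608 or BBI503 dose, and EOS is 14 days after that dose, the gap is (30 + x) − 14 = 16 + x days: 23 for x = 7, 30 for x = 14, 44 for x = 28.

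**The case against.** The strongest reply is that collection does not stop at EOS. Section 8.1 obliges investigators to document AEs in follow-up and patients to be told to report them, so a site that closed its AE log at a day-14 visit would breach the protocol. The opening of 5.10 counts safety among the things followed. The first monthly Table 3 review falls near day 30 and may involve the treating physicians. Serious AEs and persistent related AEs have explicit rules. The sentence in 10.6 also has an alternative ending, recovery from related AEs, so it is not purely a 30-day rule. Finally, the analysis is descriptive and tests no hypothesis.

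Much of this stands, and it rules out several stronger readings that a reader might infer:
- **That days 15 to 30 are unobserved, or that no AE is collected after EOS.** The provisions above contradict this.
- **That half of the safety window is lost.** The 53% is the worst case for the post-treatment tail only (steps 1 and 2).
- **That every patient is affected.** Patients with EOS on day 30 are not, and those with persistent related AEs are already in monthly contact.
- **That the comparison of arms is biased.** Nothing in the documents shows that EOS timing differs by arm.

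What the reply does not supply is a procedure. Section 8.1 creates a duty without a contact at which the question is put. Section 5.10 mentions safety, but its table has no AE item. Following known AEs does not ask other patients about new ones. The alternative ending in 10.6 does not alter the SAP's 30-day window.

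**Conclusion.** The point holds in a limited form. For patients without a persistent study-drug-related AE at EOS, new non-serious AEs, including non-serious Grade 3 events, are not actively asked about between an early EOS visit and day 30. At worst this covers 16 of the 30 post-treatment days; at best it covers none. In that interval the count relies on spontaneous reports and chart review.

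The likely effect is some under-count, with observation time set by site scheduling. Its size in events is unknown, and a difference between arms is a possibility only. The 16-day maximum assumes that the visit and the AE window share one last-dose date; step 4 shows that the texts do not guarantee this, and that the clauses tied to BBI608 or BBI503 do not clearly cover Arm 3. This should be corrected, but it does not undermine the design.

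**What to change.** 1. **Protocol 5.8 and Appendices A and B.** Keep the 14 to 30 day EOS visit and add: *If EOS is held before day 30 after the last dose, new AEs and SAEs with onset up to day 30 are collected by one telephone contact at day 30 (+7 days), in all arms.*
2. **Protocol 5.10, Table 3.** Add *new AEs to day 30* to the first monthly review.
3. **Anchor.** Define last dose identically in Protocol 5.8, 5.9.1 and 10.6 and in SAP 7.2.4.1, and state whether sorafenib counts as study drug. Without this, the call has no clear date in Arm 3 and may miss part of the SAP window in Arm 1 or Arm 2 patients who continue sorafenib.

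With a common anchor and a contact at or after day 30, the gap becomes 30 − 30 = 0 days.

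The cost is one call for each patient with an early EOS visit. The protocol already assesses AEs by telephone on Cycle 1 Day 8 and, in Phase II, on Day 15 from Cycle 3. The reported AE rate may rise slightly.
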